ANNEX 1b – Socio-economic questionnaire for CHILDREN cohorts

SCHOOL AGE CHILDREN COHORTS WP4 - Socio-economic questions for the prospective protocol (from WP8)

In the case of children, questions will be asked to the caretaker.

To be asked on Day 0:

Day 0 refers to the first contact with the patient, independently of whether they have been vaccinated, whether they are positive or negative, or of the time of infection, i.e. all cohort patients should be interviewed. It is crucial to record the date of the contact/interview.

1. (This is the ID that allows to identify the patient as part of ORCHESTRA and/or the original cohort): Patient ID _____ / Date of interview _____

Demographic information:

2. What is the school year you are attending?

Use of health care resources (COVID-19 UNRELATED/RELATED TO YOUR UNDERLYING CONDITIONS):

Since the beginning of the pandemic (February/March 2020), have you experienced:

3. any disruption in your routine visits (for eventual underlying conditions) and/or periodic check-ups (such as pediatric visits, routine vaccination schedules)?

- Cancellation Yes/No/NA
- Postponement Yes/No/NA

4. any interruption to the treatment you regularly follow?

- problems accessing medication Yes/No/NA
- Postponement of your treatment session Yes/No/NA
- Cancellation of your treatment session Yes/No/NA

Since the beginning of the pandemic (February/March 2020),

5. Were classes suspended at your school? Yes/No

If yes:

6. For how long were classes suspended?

7. Were you able to follow some forms of distance learning? Yes/No

If not:

8. Why could you not follow distance learning?

- a. distance learning was not organised at my school
- b. I was not interested/I was bored
- c. I could not rely on good technical means (e.g. computer or wifi)
- d. Other

9. In total, how many weeks of school can you estimate you have lost?

To be asked at month 6 or/and 12:

Follow-up interviews after Day 0.

1. (This is the ID that allows to identify the patient as part of ORCHESTRA and/or the original cohort): Patient ID _____ / Date of interview _____

Use of health care resources (COVID-19 UNRELATED/RELATED TO YOUR UNDERLYING CONDITIONS):

Over the last 6/12 months, have you experienced:

2. any disruption in your routine visits and/or periodic check-ups?

- Cancellation Yes/No/NA
- Postponement Yes/No/NA

3. any interruption to the treatment you regularly follow?

- Problems accessing medication Yes/No/NA
- Postponement of your treatment session Yes/No/NA
- Cancellation of your treatment session Yes/No/NA

Over the last 6/12 months:

4. Were classes suspended at your school? Yes/No

If yes:

5. For how long were classes suspended?

6. Were you able to follow some forms of distance learning? Yes/No

If not:

7. Why could you not follow distance learning?
- a. distance learning was not organised at my school
 - b. I was not interested/I was bored
 - c. I could not rely on good technical means (*e.g.* computer or wifi)
 - d. Other
8. In total, how many weeks of school can you estimate you have lost?

ANNEX 2 – Psychological scale Questionnaires

0. Time log for synchronizing analyses across cohorts and countries
1. Generalized Anxiety Disorder 7-item (GAD-7) scale
2. Perceived Stress Scale - 4 Item version
3. UCLA Loneliness Scale-short version
4. Brief Resilience Scale (BRS)
5. Depression Scale (CES-D Scale)

0. Time log for simplifying analyses across cohorts and countries [BASELINE][FOLLOW-UP]

Rational for this part: In order to compare effects of pandemic measures across different countries, we need to synchronize and include these questions about the prevention measures in place at the time assessment.

0.1 During the last two weeks have you been in a lockdown?

- | | |
|---|-----|
| 1 | Yes |
| 2 | No |

0.2 During the last two weeks have the schools been closed?

- | | |
|---|---|
| 1 | Yes |
| 2 | No |
| 3 | Not relevant for me, as I do not have children or I'm not working in a school |

0.3 During the last two weeks did you need to do home office (either completely or only on several days/week)?

- | | |
|---|-----|
| 1 | Yes |
| 2 | No |

0.4 During the last two weeks were you obliged to wear masks in closed public areas (e.g. theaters, restaurants, cinema,...)?

- | | |
|---|-----|
| 1 | Yes |
| 2 | No |

0.5 During the last two weeks were you obliged to wear masks in open public areas (e.g. parks, playgrounds,)?

- | | |
|---|-----|
| 1 | Yes |
| 2 | No |

0.6 During the last two weeks were you obliged to follow the 'vaccinated-tested-recovered' rule to:

- | | |
|---|--|
| 1 | go to work |
| 2 | go to a restaurant/bar |
| 3 | go to a shopping center |
| 4 | go to the cinema |
| 5 | go to a museum |
| 6 | go to sports events |
| 7 | go to any other place/event not mentioned before |

0.7 If '7 - go to any other place/event not mentioned before' in 0.6, please specify – open field.

0.8 During the last two weeks did you have to keep a minimum distance of 1.5 or 2 meters when contacting people outside your household?

- | | |
|---|-----|
| 1 | Yes |
| 2 | No |

1. Generalized Anxiety Disorder 7-item (GAD-7) scale [BASELINE][FOLLOW-UP]

Over the last 2 weeks, how often have you been bothered by the following problems?

| | Not at all | Several days | More than half the days | Nearly every day |
|---|-----------------------|-----------------------|-------------------------|-----------------------|
| Feeling nervous, anxious, or on edge |  |  |  |  |
| Not being able to stop or control worrying |  |  |  |  |
| Worrying too much about different things |  |  |  |  |
| Trouble relaxing |  |  |  |  |
| Being so restless that it is hard to sit still |  |  |  |  |
| Becoming easily annoyed or irritable |  |  |  |  |
| Feeling afraid as if something awful might happen |  |  |  |  |

2. Perceived Stress Scale - 4 Item version [BASELINE][FOLLOW-UP]

The questions in this scale ask you about your feelings and thoughts during the last month. In each case, please indicate with a check how often you felt or thought a certain way.

| | Never | Almost never | Sometimes | Fairly often | Very often |
|---|-----------------------|-----------------------|-----------------------|-----------------------|-----------------------|
| In the last month, how often have you felt that you were unable to control the important things in your life? |  |  |  |  |  |
| In the last month, how often have you felt confident about your ability to handle your personal problems? |  |  |  |  |  |
| In the last month, how often have you felt that things were going your way? |  |  |  |  |  |

3. UCLA Loneliness Scale-short version [BASELINE][FOLLOW-UP]

The next questions are about how you feel about different aspects of your life. For each one, tell how often you feel that way.

| | Hardly ever or never | Some of the time | Often |
|--|-----------------------|-----------------------|-----------------------|
| How often do you feel that you lack companionship? |  |  |  |
| How often do you feel left out? |  |  |  |
| How often do you feel isolated from others? |  |  |  |

4. Brief Resilience Scale (BRS) [BASELINE][FOLLOW-UP]

Please indicate the extent to which you agree with each of the following statements by using the following scale:

| | Strongly disagree | Disagree | Neutral | Agree | Strongly agree |
|--|-----------------------|-----------------------|-----------------------|-----------------------|-----------------------|
| I tend to bounce back quickly after hard times |  |  |  |  |  |
| I have a hard time making it through stressful events |  |  |  |  |  |
| It does not take me long to recover from a stressful event |  |  |  |  |  |
| It is hard for me to snap back when something bad happens |  |  |  |  |  |
| I usually come through difficult times with little trouble |  |  |  |  |  |
| I tend to take a long time to get over setbacks in my life |  |  |  |  |  |

5. Center for Epidemiologic Studies Depression Scale (CES-D Scale) [BASELINE][FOLLOW-UP]

Below is a list of the ways you might have felt or behaved. Please tell me how often you have felt this way during the past week.
During the last week ...

| | Rarely or None of the time (less than 1 day) | Some or a Little of the time (1 - 2 days) | Occasionally or a moderate amount of time (3 - 4 days) | Most or All of the time (5 - 7 days) |
|--|--|---|--|--------------------------------------|
| I was bothered by things that usually don't bother me |  |  |  |  |
| I did not feel like eating; my appetite was poor |  |  |  |  |
| I felt that I could not shake off the blues even with help from my family or friends |  |  |  |  |
| I felt that I was just as good as other people |  |  |  |  |
| I had trouble keeping my mind on what I was doing |  |  |  |  |
| I felt depressed |  |  |  |  |
| I felt that everything I did was an effort |  |  |  |  |
| I felt hopeful about the future |  |  |  |  |
| I thought my life had been a failure |  |  |  |  |
| I felt fearful |  |  |  |  |
| My sleep was restless |  |  |  |  |
| I was happy |  |  |  |  |
| I talked less than usual |  |  |  |  |
| I felt lonely |  |  |  |  |
| People were unfriendly |  |  |  |  |
| I enjoyed life |  |  |  |  |
| I had crying spells |  |  |  |  |
| I felt sad |  |  |  |  |
| I felt that people dislike me |  |  |  |  |
| I could not get "going" |  |  |  |  |

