7. OBJECTIVES

The primary objective of the ORCHESTRA fragile cohorts is to provide an extensive and harmonized collection of epidemiological and clinical data, and biological samples, to assess several features of COVID-19 in each cohort of fragile patients. These include:

- To assess the prevalence of SARS-CoV2 infection and COVID-19 disease in fragile patients;
- To describe the clinical spectrum of COVID-19 disease in different types of fragile patients;
- To analyze epidemiological, clinical and biological predictors of SARS-CoV-2 infection and prognosis in several types of fragile patients;
- To investigate the therapeutic management of COVID-19 and /or of the underlying condition and its impact on the outcome in fragile patients;

- To describe safety and efficacy of COVID-19 vaccination in selected cohorts of fragile patients;
- To describe the relationship between risk perception and adherence to preventive measures over time, including vaccine acceptance;
- To analyze the impact of COVID-19 pandemic on the use of health care services;
- To analyze the socio-economic determinants of infection and disease severity, and the socio-economic impact of the pandemic on cohort specific socio-economic indicators;
- To investigate the psychological consequences of lockdown in fragile patients.
- Identify human genetic markers and epigenetic characteristics in frail patients during post-vaccination monitoring and in the onset of breakthrough infections as well as to analyse the gut microbiome in such patients

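### Annex 2 names a four-item Perceived Stress Scale but the form shows three items, so the named four-item total cannot be formed from it

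*Protocol*

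**What the plan says.** Annex 2 of the protocol gives the title "Perceived Stress Scale - 4 Item version" twice: in the list of scales at its start and again as the heading of the form, which is marked for baseline and follow-up. The table under that heading has three question rows:

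- the first asks about a sense of lacking control over what matters in life;
- the second asks about confidence in dealing with one's own difficulties;
- the third and last reads "In the last month, how often have you felt that things were going your way".

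Every row has the same five answers to choose from: "Never | Almost never | Sometimes | Fairly often | Very often". The next form, the short UCLA Loneliness Scale, begins directly after the third row. The protocol does not mention a three-item version and gives no coding or scoring rule for this scale.

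Section 11 requires the Annex 2 questionnaires to be handed out at scheduled visits. They serve one of the objectives in section 7: "To investigate the psychological consequences of lockdown in fragile patients".

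**The concern.** The form contradicts its own title. If it is fielded as shown, one item of the named instrument is never asked, and this recurs at every baseline and follow-up administration. A later scoring rule cannot recover an answer that was not collected.

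The practical risk lies in pooling. Annex 2 explains its opening block of questions on prevention measures by the wish to compare the effects of those measures between countries. If one cohort uses the form as shown and another uses a complete four-item form, their sums have different ranges but carry the same scale name.

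**Working it through.** **Inputs.** From Annex 2: four items in the title, three items in the table, five answers per item. The answer coding is not in the protocol, so 0-4 and 1-5 are both taken as assumptions.

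**Item count against title.**
- Perceived Stress Scale: 4 named, 3 shown. Mismatch.
- GAD-7, the only other Annex 2 scale with an item number in its name: 7 named, 7 shown. Match.
- UCLA short form, Brief Resilience Scale and CES-D: 3, 6 and 20 items shown. The protocol states no expected number for these, so they cannot serve as a check.

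**Range of the sum** (number of items × lowest code, to number of items × highest code).
- Coding 0-4: three items run from 3 × 0 = 0 to 3 × 4 = 12; four items run from 4 × 0 = 0 to 4 × 4 = 16.
- Coding 1-5: three items run from 3 × 1 = 3 to 3 × 5 = 15; four items run from 4 × 1 = 4 to 4 × 5 = 20.

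**Shortfall per person.** Let S3 be the sum of the three items shown and x the score of the absent item, all coded in the same direction. The four-item total is S4 = S3 + x, so S4 − S3 = x. The shortfall is 0 to 4 points under 0-4 coding and 1 to 5 points under 1-5 coding.

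**Why no average percentage follows.** The ratio of the maxima is 12/16 = 15/20 = 0.75. The ratio of the mean sums is 3m/(3m + m4), where m is the mean of the three items shown and m4 the mean of the absent one. It equals 0.75 only if m4 = m. As an illustration, take m = 2, the midpoint of 0-4 coding. With m4 = 0 the ratio is 6/6 = 1 (no shortfall), and with m4 = 4 it is 6/10 = 0.60 (40% lower). The protocol has no information on m4.

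**Direction of wording.** In the first item shown, a more frequent answer means more stress. In the other two it means less. A sum or mean is interpretable only after one direction is reversed: 4 minus the answer under 0-4 coding, or 6 minus the answer under 1-5 coding.

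**Reach.** Perceived stress is not among the endpoint variables in section 12. The scale is also not among the mental health instruments listed for Table 1 of the schedule of assessments (footnote 18: HADS, K10, IES-R and RSA).

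**The case against.** The strongest objection is that the row may have been lost when the PDF was read. A broken table is not an error in the plan. That the table looks whole in the extracted text proves little, since a row dropped during extraction would leave no trace. This stands as a caveat, and it is why the first step is to check the original form.

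A reader might infer that the other Annex 2 scales are all demonstrably complete, which would make a lost row implausible. The protocol does not support that: only GAD-7 states a number to compare with, so the supporting pattern is a single scale.

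A reader might also infer that three-item sums run 25% lower on average. The 25% is the loss of maximum; as an average it needs an assumption about the unasked item that the documents do not supply.

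Nor does it follow that the data would be useless for comparison. Cohorts using the same three items would still be compared like with like, and the protocol plans no comparison with outside reference values for this scale.

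Finally, scoring rules may properly sit in a statistical analysis plan that is not at hand. That is accepted, but which items are put to participants is fixed by the form in the protocol, and the mismatch lies there.

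**Conclusion.** The point holds in a limited form. As read, Annex 2 titles the scale as four items and shows three, and the named total cannot be formed from what is shown. The maximum is 12 instead of 16 under assumed 0-4 coding, or 15 instead of 20 under assumed 1-5 coding. Each person's shortfall is the unasked item's score.

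The conclusion rests on the extracted table being faithful to the original. The documents do not show that participants were in fact given three items. The consequence is limited to the lockdown psychology objective and does not touch the section 12 endpoints. This is a minor correction.

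**What to change.** Check the original Annex 2 and the form actually fielded at each cohort.

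- If the fielded form has three items, add the missing item of the named version for all further baseline and follow-up use. Report forms already collected as a three-item version, scored as the item mean after reverse-coding the oppositely worded items. Do not pool them as sums with four-item totals.
- If the fielded form has four items, correct Annex 2 so that the form matches its title.

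The cost is the form check, one questionnaire row and a short scoring note.

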ANNEX 3 – Questionnaire for monitoring of adverse events to COVID-19 vaccination

A) Demographics – Anamnesis

Age: _____

Sex: M F

Special population: HIV Cancer Solid organ transplant Haematological stem cell transplant

If solid organ transplant, please specify: Liver Kidney Heart Lung

Drug/food allergies: Y N If yes, please specify: _____

Previous serious adverse events to vaccination: Y N

Underlying diseases:

Renal Cardiovascular Asthma Diabetes mellitus Anaemia/Blood disorders

Seizure/Epilepsy

Other nervous system disease: Y N If yes, please specify: _____

Concomitant medications: _____

Blood transfusion in the last year: Y N

Treatment with immunoglobulin or antivirals in the last year: Y N

Other relevant conditions: _____

B) Adverse event report

First dose (dd/mm/yy): _____

Second dose (dd/mm/yy): _____

Clinical events after the first dose: Y N

Clinical events after the first dose: Y N

Headache: Y N

Asthenia: Y N

Fever ($\geq 38^{\circ}\text{C}$): Y N

Nausea: Y N

Vomiting: Y N

Lymphadenopathy: Y N

Tachycardia: Y N

Flushing: Y N

Syncope: Y N

Pruritus, erythema or pain in injection site: Y N

- Generalised urticaria: Y N
- Serious allergic events (anaphylaxis, angioedema): Y N
- COVID infection after vaccination: Y N
- Use of paracetamol or non-steroidal anti-inflammatory drugs: Y N
- Requirement for use of other drugs: Y N If Yes, please specify: _____
- Demyelinating disorders: Y N
- Encephalitis/Encephalopathy: Y N
- Peripheral neuropathy: Y N
- Muscular weakness and/or paralysis: Y N
- Visual impairment (including optic neuritis): Y N
- Walking disturbance: Y N
- Blood disorders (anaemia, thrombocytopenia, leukopenia): Y N
- Seizures/Epilepsy: Y N
- Weakness and/or paralysis of facial muscle: Y N
- Vasculitis: Y N
- Renal disorders: Y N
- Liver function disorders: Y N
- Cardiac disorders: Y N
- Other adverse events: Y N If Yes, please specify: _____

[figure not shown]
If yes (complete for each reported event): day of onset (dd/mm/yy): _____

hospitalization/emergency department admission/general practitioner visit: Y N

Description of the event (laboratory data/administered drugs/other relevant information):

Recovery: Y N

ANNEX 4 – WP6 Deliverable 6.1_Mapping of retrospective samples and development of standardized protocols for prospective sampling

WP6 Deliverable 6.1

Mapping of retrospective samples and development of
standardised protocols for prospective sampling

UANTWERPEN

Project Classification

| | |
|--------------------------------|---|
| Project Acronym: | ORCHESTRA |
| Project Title: | Connecting European Cohorts to Increase Common and Effective Response to SARS- CoV-2 Pandemic |
| Coordinator: | UNIVR |
| Grant Agreement Number: | 101016167 |
| Funding Scheme: | Horizon 2020 |
| Start: | 1st December 2020 |
| Duration: | 36 months |
| Website: | www.orchestra-cohort.eu |
| Email: | [contact] |

Document Classification

| | |
|--------------------------------------|---|
| WP No: | WP6 |
| Deliverable No: | D6.1 |
| Title: | Standardised protocol and manual on collection and storage of samples |
| Lead Beneficiary: | UANTWERPEN |
| Other Involved Beneficiaries: | UNIBO, INSERM, HMGU |
| Nature: | Report, |
| Dissemination Level: | Confidential |
| Due Delivery Date: | M6 / 31 May, 2021 |
| Submission Date: | 31 May, 2021 |
| Justification of delay: | N/A |
| Status: | Final |
| Version: | 1.0 |
| Author(s): | [name], [name] |

History of Changes

| Version | Date | Created/Modified by |
|---------|------|--|
| 1 | | [name], [name] |

Table of contents

| | |
|-------------------------------|---|
| Executive summary | 3 |
| WP Context..... | 3 |
| Purpose of the document | 3 |
| Content of the document | 3 |
| Target of the document | 4 |
| Dissemination level..... | 4 |
| Core content..... | 4 |
| References | 4 |
| Acknowledgments | 4 |
| Appendix 1..... | 5 |

Executive summary

WP Context

The objective of WP6 in the ORCHESTRA project is to study human (epi)genetic, immunological, microbial, and viral features to identify markers of disease severity and to study the long-term impact of SARS-CoV-2 infection as well as the effect of immunization and characteristics underlying breakthrough infections post vaccination. Samples will be included retrospectively as well as prospectively within the study to study severe COVID-19 infection in hospitalized and outpatients during the acute disease stage as well as study long-term effects of infection and immunization on the host immune response.

Purpose of the document

The purpose of the WP6 protocols is to provide an overview of the biosamples to be collected within the prospective ORCHESTRA study, at which timepoints, and which analyses these samples are to be subjected to.

Content of the document

The WP6 protocol outlines the objectives of the biological studies foreseen within the project, the methodology to be utilized to meet these goals, which patient populations that are to be analyzed, and how these samples are to be handled and stored.

Target of the document

The target audience of the document are the clinical WPs 2-5 within the ORCHESTRA study in which prospective sample collection is conducted.

Dissemination level

Confidential, only for members of the consortium (including the Commission Services).

Core content

The WP6 prospective protocol document is available in Appendix 1.

References

N/A

Acknowledgments

N/A

Appendix 1

PROSPECTIVE SAMPLE COLLECTION AND MANAGEMENT DOCUMENT

WP6 – Biobanking, genomics, and viral-host interactions

University of Antwerp (UANTWERPEN) in collaboration with all WP6 partners

Version dated 11-05-2021

Thank you for your participation in the ORCHESTRA study. The purpose of this document is to provide you with additional information and instructions on the collection and processing of samples for WP6 within the prospective tier of ORCHESTRA. This document is a guideline for research staff including (sub-) investigators, research nurses, and laboratory staff. The clinical protocol takes precedence over this document. If there is a discrepancy between the sample collection and management document and the clinical protocol, the ORCHESTRA clinical protocol should be followed.

This document outlines how samples should be handled after patient inclusion. Specifically, it describes the time points desired for biosampling.

Project Classification

| | |
|-------------------------|---|
| Project Acronym: | ORCHESTRA |
| Project Title: | Connecting European Cohorts to Increase Common and Effective Response to SARS- CoV-2 Pandemic |
| Coordinator: | UNIVR |
| Grant Agreement Number: | 101016167 |
| Funding Scheme: | Horizon 2020 |
| Start: | 1st December 2020 |
| Duration: | 36 months |
| Website: | www.orchestra-cohort.eu |
| Email: | [contact] |

Document Classification

| | |
|-------------------------------|--|
| Title: | PROSPECTIVE SAMPLE COLLECTION AND MANAGEMENT DOCUMENT |
| Lead Beneficiary: | UANTWERPEN |
| Other Involved Beneficiaries: | INSERM, APHP, UNIBO, HMGU |
| PIs, Participating centres | [name], UANTWERPEN [name], UANTWERPEN [name], UNIBO [name], UNIBO [name], INSERM/APHP [name], INSERM [name], HMGU |
